## **Comparison of three different tissue acquisition techniques during endoscopic ultrasound-guided fine needle biopsies of solid lesions: A randomized single blind clinical trial.**

### **ABSTRACT**

- a. Endoscopic ultrasound guided fine-needle aspiration (EUS-FNA) has been used since 1990's for the diagnosis and staging of esophageal, gastric, duodenal, pancreatobiliary, rectal mediastinal lesions and intra-abdominal lymphadenopathy. Studies have shown a variable range of specimen adequacy when performing pancreatic biopsies with the standard fine needle aspiration (FNA) needles with this modality. There are several factors that affect the overall diagnostic yield of this procedure, such as endosonographer experience, presence of cytopathologist during the procedure, the needle diameter and the number of passes. In this study we will compare the yield of recently available fine biopsy needles (FNB) using three different techniques to obtain samples from solid lesions. All solid lesions will be studied with the endoscopic ultrasound. If during the procedure the characteristics of the lesion are comfortably determined and it is decided that it does not need a biopsy, then it won't be done (i.e. lipomas). These lesions are very well determined on EUS and do not need a biopsy. The three techniques to be compared in this study are: stylet slow pull (SP) vs dry suction (DS) vs wet suction (WS).

### **OBJECTIVES**

The primary objective of this study is to compare the rate of adequacy for cytologic and/or histologic diagnosis of specimens obtained using three different techniques of tissue acquisition when performing EUS guided sampling of solid lesions with FNB needles. The three techniques to be compared are: SP, DS and WS. The secondary objectives are to compare the rate of blood contamination of the specimen obtained by each technique

### **BACKGROUND**

Endoscopic ultrasound guided fine-needle aspiration (EUS-FNA) has been used since 1990's for the diagnosis and staging of esophageal, gastric, duodenal, pancreatobiliary, rectal and mediastinal lesions and intra-abdominal lymphadenopathy . Studies have shown a variable range of specimen adequacy when performing pancreatic biopsies with the standard fine needle aspiration (FNA) needles with this modality . When sampling the lesions, the use of a stylet and/or suction during FNA of solid lesions has been used to increase the accuracy, efficiency and quality of the specimen. Theoretically, the use of a stylet prevents obstruction of the needle lumen as it penetrates the gastrointestinal wall tissue, resulting in less contamination from GI wall cells .

In the "suction technique" the stylet of the needle can be left in place or removed before puncturing the lesion. Once the needle is inside the target, negative pressure is applied through a 10 or 20 cc syringe connected to the needle. This technique has yielded adequate specimens in

approximately 70% of cases in some studies, with no difference seen between the stylet vs no stylet modality. Some alterations of this technique have been used. In cases of neuroendocrine tumors especially, no suction techniques have been tried to avoid the effect of dilution by too much bleeding in such highly vascular tumors. In a recent study on 52 patients, the accuracy was higher utilizing the suction technique compared to no suction. The bloodiness of the samples was not different in each arm. The lesions were located in the mediastinum, pancreas, adrenals and others. Another study on 100 patients in 2014 did not report any difference in the adequacy of samples obtained with or without suction. The samples were more contaminated with blood in the suction group though. It has been concluded that at the expense of a bloodier sample, suction method yields a high cellular material. The wet suction technique consists of flushing of the needle with 5 ml of saline solution to replace the column of air within the lumen of needle with saline solution before needle aspiration. Once the needle is flushed, negative pressure is applied with a 10 or 20 cc syringe connected to the needle. This novel technique was compared with the conventional FNA technique by using 22-gauge needles. A total of 117 samples from 95 patients and 72 lesions were obtained in an alternating pattern between the two techniques. If the first pass was done by wet suction then the second one was done by the FNA conventional method. Higher cellularity scores and adequacy of specimen were achieved with wet suction (68% vs 44%, respectively) and (85% vs 75, respectively). However, the diagnostic yield difference was not specified.

In the slow pull technique, the stylet is left in place in the needle and is slightly retracted prior to puncturing the lesion. Once the needle is inside the target, the stylet is pushed completely into the needle to remove any contaminant cells and several back and forth movements are done while slowly withdrawing the stylet. One study compared slow pull technique versus suction. Although scores of cellularity were lower in the slow pull group (A score of more than or equal 2 in 37.5% vs 76.7%), the contamination of samples observed was lower (25% vs 66.7%). The accuracy and sensitivity of the slow-pull technique were significantly higher than those of the suction techniques for solid pancreatic lesions. Specifically for malignancy, the slow pull technique has demonstrated sensitivity for diagnosis of 90% compared to 68% with the suction technique. (12) Moreover, this technique showed less false negatives results than suction (11 vs 26%)(14 ABSTRACT).

Recently new fine needle biopsy (FNB) needles have become widely available in the US. These needles differ from FNA needles in its design and allow for long cores of tissue to be obtained. Recent studies have already suggested that samples obtained with these needles are superior to the ones obtained with standard FNA needles. Given the novelty of these FNB needles, literature regarding different techniques of tissue acquisition with them is scarce. Therefore, in this study we aim to compare the cellularity of specimens obtained with these needles using the three different techniques described above in a randomized fashion.

## **RESEARCH PLAN**

### **Study Design**

This study is planned as a single-blind, parallel group randomized clinical trial (RCT). After receiving consent from the eligible subjects, the subjects will be randomly assigned to one of the three techniques and one of two needles, stratified by the three (3) endoscopists performing EUS-FNB.

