## **METHODS**

Patients will be enrolled in a prospective manner at the University Medical Center of El Paso endoscopy unit. At the time of the pre-op appointment the nurse will perform the usual evaluation of the patient and will explain the EUS/FNB procedure. The day of the procedure, the endoscopist performing the procedure explain the EUS/FNB procedure and the risks of the procedure, explain the study and will consent the patients. He will randomize them using a random number list generated by a simple block randomization scheme by our study statistician, to one of three possible groups: SP, DS or WS. The randomization number will be kept in sealed opaque envelopes in numerical sequence. The random number sequence will be generated using SAS software. The patients will be asked to sign the consent only after the study has been explained to them and all their questions have been answered by the performing physician. The randomization will be via sealed envelopes that will contain cards with the technique and the needle to be used. Following randomization each patient will be assigned a code corresponding to one of the three technique arms. This code will be noted and placed in a master spreadsheet that only the study coordinator and/or assigned research personnel will handle.

All the procedures will be performed by three experienced endoscopists ([name]., [name]. and [name].) using 22 gauge SharkCore™ (MEDTRONIC) or Acquire™ (BOSTON SCIENTIFIC) FNB needles. The techniques to be used are described here:

DS: the stylet will be left in place in the needle and once the lesion has been punctured, the stylet will be withdrawn. After this, negative pressure with a 10 cc syringe will be applied to the needle. Once the lesion has been punctured, the valve between the syringe and the needle will be opened and the endoscopist will obtain the sample with multiple back and forth movements.

SP: the stylet will be left inside the needle and retracted slightly prior to puncturing the lesion in order to sharpen the needle. Once the lesion has been punctured, the stylet will be pushed completely into the needle to expel any debris from the gastrointestinal wall, then it will be

5/7/2020

slowly withdrawn from the needle as the endoscopist is making the back and forth movements to create negative pressure in the system.

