WS: Prior to puncturing the needle, the stylet will be completely withdrawn and the needle will be flushed with 10 cc of normal saline until the entire needle lumen is completely primed with fluid. After this, negative pressure with a 10 cc syringe containing 1 cc of NS will be applied in a similar manner as in the DS technique. The procedures will be performed under deep sedation according to the principles of monitored anesthesia care. The patients will be anesthetized with intravenous administration of propofol by trained anesthesiologists. Once the lesion is evaluated by EUS, the endoscopist will select the shortest pathway, while avoiding blood vessels, to reach the pancreatic lesion. Under real-time visualization, each lesion will be punctured with 3 needle passes.

If the tissue sample is deemed suboptimal after these 3 passes, then the endoscopist will be allowed to use a different needle and/or technique according to his preference. The specimen obtained will be assessed preliminarily by the cytology technician who will determine if more tissue is needed. Once the tissue is deemed to be sufficient, the pathologist evaluating the specimen will dictate the official cellularity and blood contamination scores according to scales previously described by Gerke et al  and Wee et al . These will be the scores used for analysis. A score of  $\geq 2$  and  $\geq 4$  will be considered adequate for cytological and histological diagnosis respectively. The pathologists evaluating the sample will be blinded to the type of needle and technique used.

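### The plan does not hold the envelope back until EUS has confirmed a biopsy, so it permits, without establishing, that an operator who knows the arm decides whether a randomised patient yields a specimen

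*Combined protocol and SAP*

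**What the plan says.** Study Design sets the order: "After receiving consent from the eligible subjects, the subjects will be randomly assigned to one of the three techniques and one of two needles". METHODS says that the endoscopist who will do the procedure takes consent that day, and then: "He will randomize them using a random number list generated by a simple block randomization scheme by our study statistician". On the envelopes it adds: "The randomization will be via sealed envelopes that will contain cards with the technique and the needle to be used". It goes on: "Following randomization each patient will be assigned a code corresponding to one of the three technique arms".

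The ABSTRACT provides for a biopsy that is not taken: "If during the procedure the characteristics of the lesion are comfortably determined and it is decided that it does not need a biopsy", then none is done. Lipomas are the example. EUS evaluation appears later in METHODS, as a step before the needle path is chosen: "Once the lesion is evaluated by EUS, the endoscopist will select the shortest pathway".

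On blinding, METHODS says: "The pathologists evaluating the sample will be blinded to the type of needle and technique used". Nothing blinds the endoscopist, who has to know the technique in order to perform it.

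The primary endpoint is the rate of adequate specimens by technique. The Statistical Analysis paragraph names no analysis set and no rule for a randomised patient without a specimen. Patient Enrollment gives 300 patients without saying whether they are counted at randomisation or at biopsy.

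**The concern.** Whether a lesion is clear enough on EUS to need no biopsy is a judgement. In a trial whose operator cannot be blinded, that judgement is protected only if the assignment is still concealed when it is made. If the card has already been read, knowledge of the technique and needle could enter the decision. The patients who contribute specimens could then differ between arms for a reason other than chance.

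Such a patient would also be randomised but have no specimen. The plan does not say whether he or she is removed, replaced or counted as inadequate, and each choice gives the primary comparison a different denominator.

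**Working it through.** **The text, side by side**

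1. *When.* Study Design and METHODS place randomisation after consent. No section places it before or after EUS evaluation, so opening the envelope before EUS is allowed but not stated.
2. *Who.* One person takes consent, randomises, performs EUS and decides on biopsy. If the card is opened before EUS, that person knows the arm when deciding.
3. *What is counted.* The endpoint is a rate among specimens. A patient with none is not provided for.
4. *What is recorded.* The arm code, with the number of passes on the data list, would let unbiopsied patients be counted by arm. The EUS characteristics on the same list (number, location, size, echogenic pattern, invasion) are the kind of finding on which the ABSTRACT bases the decision, so they would partly explain it. There is no field for the reason itself.

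**Does loss of such patients threaten power?**

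Inputs from the sample size paragraph: 45% against 70%, two-sided 1%, pooled Z-test, 95 per group for more than 80% power; and means 1.85, 1.70 and 1.45 (SD 0.79, 0.72, 0.78), one-way ANOVA at 1%, 100 per group for 80% power.

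Z-test: power = Φ{[|p2 − p1| − 2.576·√(2p̄(1−p̄)/n)] / √([p1(1−p1) + p2(1−p2)]/n)}, with p̄ = 0.575. At the plan's n = 95 the null term is 2.576 × √(0.48875/95) = 0.1848 and the denominator is √(0.4575/95) = 0.0694. So (0.25 − 0.1848)/0.0694 = 0.94, and power is 82.6%. The plan's statement is reproduced.

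ANOVA: λ = n·Σ(m − m̄)²/SD², where m̄ = 1.6667 and Σ(m − m̄)² = 0.0817, on 2 and 3n − 3 degrees of freedom. The plan gives no common SD; averaging the three gives 0.76 (rounded) or 0.7633, and their root mean square is 0.764. At n = 100 and SD 0.7633, λ = 8.167/0.5826 = 14.0 and power is 79.7%, which reproduces the stated 80%.

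The documents give no rate of cancelled biopsies, so the losses below are assumptions.

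| Per group | Assumed loss from 100 | Z-test | ANOVA (SD 0.764 to 0.76) |
|---|---|---|---|
| 100 | 0% | 84.9% | 79.6% to 80.1% |
| 95 | 5% | 82.6% | 76.9% to 77.4% |
| 90 | 10% | 80.1% | 73.9% to 74.4% |

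The Z-test keeps about 80% up to a 10% loss. The ANOVA, which the plan uses to validate the sample size, has no reserve. At 1% loss (99 per group) the Z-test has 84.5% and the ANOVA loses about 0.5 points.

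**Can the bias be sized?**

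Not from the documents. As a hypothetical only: let both arms have a true rate of 45%, and remove 5 of 100 patients from one arm, all of whom would have been inadequate. That arm shows 45/95 = 47.4%, a false gain of 2.4 points, and the nominal 1% test rejects 1.4% of the time. With 10 removed the figures are 45/90 = 50.0%, 5.0 points and 3.0%. This assumes an operator who can pick out failures before any specimen exists, so it is not an estimate for this trial.

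**The case against.** The strongest reply is that assignment after consent fixes an order, not a time. Consent must come before sedation in any design, so the wording fits an envelope opened after EUS equally well. The technique descriptions begin at needle preparation or puncture, which sits easily with late opening. Only eligible subjects are randomised, eligibility requires a need for tissue sampling, and a lesion found not to need biopsy arguably fails that criterion. No section says that an unbiopsied patient is dropped. All of this stands, and it limits the point to what the text allows.

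Four stronger readings might be inferred, and the documents support none of them:

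- *Envelopes are opened before EUS, or operators will drop patients by arm.* The time of opening is unstated, and nothing suggests such conduct.
- *The plan admits that operator preference is at work.* The clause "the endoscopist will be allowed to use a different needle and/or technique according to his preference" applies once three passes have given a suboptimal sample. It says nothing about cancelling a biopsy.
- *An imbalance could not be explained.* The recorded EUS characteristics would explain it in part.
- *The trial would be underpowered.* The losses are assumed, and at the low rates that the text suggests they hardly matter.

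Two further replies also stand. The missing analysis set is a general omission whenever envelopes are opened, and adds no weight to a worry about operators. And late opening does not stop an endoscopist from guessing later assignments, since allocation is in blocks and stratified by endoscopist.

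**Conclusion.** The point holds as a gap in the design rule, not as a demonstrated flaw. The text permits an unblinded operator to decide whether an already randomised patient contributes to the primary outcome, and gives that patient no place in it. This rests on the silence about envelope timing; if local practice already opens the envelope after EUS, one sentence settles the matter. The event is probably rare, and the size of any bias is unknown. The point is still worth acting on, because delaying the envelope is a better rule than randomising at any time after consent. It keeps arm knowledge out of the biopsy decision and prevents post-randomisation loss from this cause. It is a cheap improvement that the sponsor should make.

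**What to change.** Leave consent as it is. In Study Design and METHODS, state that after EUS evaluation the endoscopist records the decision to biopsy, that only then is the next sealed envelope opened, and that the 300 are counted from that opening. Patients who consent but are found not to need a biopsy are then reported as not randomised.

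If envelopes are to be opened before EUS, the plan should say so, add to the data list whether a biopsy was done and, if not, why, define the analysis set for these patients, and report them by arm.

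The cost is a few sentences of wording, both needle types at hand in the room, and a short pause under sedation while the envelope is opened and the needle prepared. Slightly more than 300 consents would be needed: 300/0.99, 300/0.95 and 300/0.90 give 304, 316 and 334 at assumed non-biopsy rates of 1%, 5% and 10%. Guessing of assignments within blocks is not addressed by this change.

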Statistical Analysis: All categorical variables will be described using count and percentage whereas the quantitative variables will be described using mean and standard deviation(SD). The baseline characteristics will be compared among three groups using either one way analysis of variance (for quantitative data) or Fisher's exact tests (for categorical data). The primary outcome (cellularity score: quantitative and categorical forms and percentage positive diagnostic yield) will be compared between groups using an F-test or Fisher's exact tests. The proportion differences between two groups will be compared using two sided Z-test between two groups

while quantitative scores will be compared using t-tests with Bonferroni corrected method. The effect size will be summarized using proportion difference along with 95% confidence interval (CI) estimated using Binomial distribution. Further, relative risk regression analysis will be performed for determining adjusted differences in cellularity and diagnostic yields between groups. The regression analysis will be carried out separately for each outcome. This analysis will also help to identify any factors associated with increased percentage of cellularity and diagnostic yield. The secondary outcomes will also be compared between groups using a Fisher's exact test or an F-test depending on the type of outcome. The results of relative risk regression analysis will be summarized using relative risk along with 95%CI and p-value. P-values less than 5% will be considered statistically significant results. All the statistical analyses will be processed using STATA 14 and SAS 9.4.

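### The primary tests and intervals ignore the endoscopist strata and the randomised needle, which gives up a small, cheap gain in precision; the adjusted regression names no covariates

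*Combined protocol and SAP*

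**What the plan says.** Under Study Design, patients are "randomly assigned to one of the three techniques and one of two needles, stratified by the three (3) endoscopists". The Abstract says "There are several factors that affect the overall diagnostic yield of this procedure, such as endosonographer experience", so the authors themselves treat the operator as potentially prognostic.

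Under Statistical analysis, the primary outcome "will be compared between groups using an F-test or Fisher's exact tests". For pairs, "The proportion differences between two groups will be compared using two sided Z-test between two groups", and "quantitative scores will be compared using t-tests with Bonferroni corrected method". On estimation, "The effect size will be summarized using proportion difference along with 95% confidence interval (CI) estimated using Binomial distribution". None of these mentions endoscopist or needle. A relative-risk regression "will be performed for determining adjusted differences in cellularity and diagnostic yields between groups" is then added. It is summarised as a ratio, and its covariates are not listed. The closing rule is "P-values less than 5% will be considered statistically significant results", whereas the sample size was set at a 1% level.

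Two other sections bear on this. METHODS describes a simple block scheme to the three techniques without mentioning strata, although the envelope cards carry both technique and needle. The Data Collection list contains neither endoscopist nor needle.

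**The concern.** Stratified allocation balances the arms within each endoscopist, so differences between operators cannot contribute to the technique contrast. A crude test or interval still counts those differences as noise. If the factors predict adequacy, the standard error is too large, the test rejects less often than its nominal level, and the interval covers more than 95%. The result is still valid, but precision that the design has already secured goes unused.

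The regression does not settle this. A ratio does not replace the proportion difference chosen as the effect measure. With no covariates named, the adjusted result cannot be reproduced from the plan and can be chosen after the data are seen.

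**Working it through.** **Inputs from the plan.** 45% vs 70% (the 25% read as absolute), two-sided 1% level, pooled Z-test and 95 per group; for the score, means 1.85, 1.70 and 1.45 with SDs 0.79, 0.72 and 0.78 and 100 per group. All are in the sample size paragraph.

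**The plan's own figures.**
- Pairwise: the pooled rate is 0.575. The null SE is √(2 × 0.575 × 0.425 / 95) = 0.0717 and the alternative SE is √((0.45 × 0.55 + 0.70 × 0.30) / 95) = 0.0694. Power = Φ((0.25 − 2.576 × 0.0717) / 0.0694) = Φ(0.94) = 82.6%. More than 80% is confirmed. At 100 per group it is 84.9%.
- Score: with common SD 0.764 (root mean square of the three SDs), the noncentral F at 1% with 100 per group gives 79.6%, in line with the stated 80%.

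**Assumptions for the comparison.** The documents give no operator or needle effect, so four settings were used, on the log-odds scale (operators at −e, 0, +e; needles at −d, +d):
- None.
- Small: e = 0.3, d = 0.3. Adequacy in the 45% arm is 38/45/52% by operator and 38/52% by needle.
- Large: e = 0.75, d = 0.6. By operator 29/45/62%.
- Extreme: e = 1.2, d = 0.6. By operator about 21/44/70%.

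The intercept is solved in each arm so that the overall rates stay at 45% and 70%. Allocation is balanced over the six endoscopist-by-needle cells at 16 per cell, hence 96 per arm, the number nearest 95 that divides by six.

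**Interval width by formula.** The crude half-width is 1.96 × √(0.4575 / 96) = 13.5 points. The stratified half-width replaces 0.4575 with the sum over the two arms of the mean within-cell p(1 − p). That sum is 0.4575, 0.442, 0.395 and 0.359 in the four settings, giving 13.5, 13.3, 12.6 and 12.0 points.

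**Simulation, 200,000 trials per setting.** Crude pooled Z against the Cochran-Mantel-Haenszel (CMH) test without continuity correction, for one pair of techniques:

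| Setting | Power at 1%, Z / CMH | Power at 5%, Z / CMH | Type I error at 1%, Z / CMH | Coverage of crude 95% CI |
|---|---|---|---|---|
| None | 83.8 / 83.7 | 94.3 / 94.3 | 1.15 / 1.10 | 95.0 |
| Small | 84.2 / 84.6 | 94.6 / 94.9 | 0.95 / 0.98 | 95.4 |
| Large | 85.5 / 89.2 | 95.6 / 96.9 | 0.59 / 1.00 | 96.5 |
| Extreme | 86.7 / 92.2 | 96.2 / 97.9 | 0.37 / 0.97 | 97.3 |

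The stratified interval covers 94.8 to 95.0% throughout.

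**Three-group test at 5%**, Pearson chi-square (standing in for Fisher) against generalised CMH, same order of settings:
- 45/45/70%: 96.5/96.5, 96.7/97.0, 97.3/98.3, 97.7/99.0.
- 45/57.5/70%: 89.9/89.8, 90.1/90.6, 91.1/93.7, 91.9/95.7.

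**Score F-test at 1%**, 96 per group, crude against a model with both terms, when the two factors explain 0, 2, 5 or 10% of the variance: 77.5/77.5, 77.5/78.5, 77.7/80.1, 78.0/82.8.

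**Sensitivity.**
- Unequal operator volumes (48/32/16 per arm): pairwise Z/CMH at 1% is 83.7/83.6, 84.1/84.5, 85.5/88.7, 86.2/91.0.
- Unstratified allocation: 83.6/81.8, 83.8/83.5, 83.8/88.1, 83.7/91.3. Crude coverage is then nominal (94.8 to 94.9%).

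**The case against.** The best case for leaving the plan alone has five parts.

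- **The harm is small.** The crude analysis is valid, errs on the safe side and meets its stated power. This stands; the point is about efficiency and specification, not validity.
- **The larger gains rest on settings the documents do not support.** Even the small setting has a 14-point spread across operators, over half the 25-point technique effect, and gains only about half a power point. METHODS calls all three endoscopists experienced, which weakens the Abstract's remark as evidence of a large operator effect. This also stands.
- **At the 5% analysis level the pairwise gain shrinks** to 0, 0.3, 1.3 and 1.7 points. That is correct, and the table shows it.
- **The conservatism depends on balance within cells.** Study Design stratifies by endoscopist only, with needle randomised alongside, and METHODS mentions no strata at all. If allocation is unstratified, the crude interval has nominal coverage and CMH loses 1.8 points with no effects and about 0.2 at the small setting. So the low cost is conditional, and the randomisation wording should be settled first.
- **An adjusted regression is already planned.** Endoscopist and needle would be natural covariates there, so for that analysis adjustment is unspecified rather than excluded. But an unnamed set is not prespecified, and the primary tests and interval stay crude in any case.

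The simulation also used a chi-square for Fisher's test, a Wald form for the binomial interval, and 96 rather than 100 per arm. A separate calculation at 100 per arm with other odds ratios gave the same pattern: a cost of about 0.3 points with no effects, and gains up to about 4.5 points. None of this changes the direction.

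**Conclusion.** The concern holds, as an improvement the plan should make rather than a threat to the trial. The design stratifies by endoscopist and randomises needle; the primary tests and intervals use neither, and the adjusted analysis is not specified well enough to reproduce. With balanced allocation, stratifying costs essentially nothing when the factors do not matter and restores nominal type I error and coverage when they do. The realistic gain is probably small: about half a power point at the 1% level and 0.2 points of half-width under the small setting. The upper figures depend wholly on assumed operator and needle effects. The need to name the covariates does not depend on the size of those effects.

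**What to change.** 1. Align METHODS with Study Design: state that blocked lists of the six technique-by-needle combinations are prepared within each endoscopist, if that is what is done.
2. Make the primary adequacy comparison stratified by endoscopist (3 levels) and assigned needle (2 levels): generalised CMH for three groups, CMH for pairs. Keep the crude tests as supportive.
3. Replace the crude binomial interval with a stratified (Mantel-Haenszel or equally weighted) proportion difference and its 95% CI.
4. Add the same two terms to the F- and t-test models for the score, keeping the Bonferroni correction, and name them in the relative-risk regression.
5. Add endoscopist and assigned needle to the Data Collection list. Analyse the assigned needle, since METHODS permits a change after three passes; the item on other manoeuvres can record that change.

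The cost is SAP wording and two variables already known at randomisation, with no extra patients. If allocation proves to be unstratified and neither factor predicts adequacy, the price is about 1.8 points of pairwise power (83.6% to 81.8%), 0.4 to 0.8 points for the three-group test, and a half-width of 13.7 instead of 13.5 points.

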### **Primary endpoint**

1. Compare the rate of adequate specimens obtained by slow pull vs dry suction vs wet suction techniques using the new fine needle biopsy (FNB) needles in solid lesions.

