### **Secondary outcome**

1. Compare the degree of blood contamination obtained by all three techniques.

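### Needle is randomised alongside technique, but no needle comparison and no check that technique effects agree across needles is planned

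*Combined protocol and SAP*

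**What the plan says.** Under Study Design, patients are "randomly assigned to one of the three techniques and one of two needles", "stratified by the three (3) endoscopists performing EUS-FNB". METHODS agrees: randomisation uses "sealed envelopes that will contain cards with the technique and the needle to be used". It names two 22-gauge needles from different manufacturers and says the pathologists are blinded to needle as well as technique.

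The rest of the plan has one factor. METHODS also describes randomisation "to one of three possible groups: SP, DS or WS", and afterwards "each patient will be assigned a code corresponding to one of the three technique arms". The primary endpoint is to "Compare the rate of adequate specimens obtained by slow pull vs dry suction vs wet suction techniques", with the needles taken together as a class. The secondary outcome is to "Compare the degree of blood contamination obtained by all three techniques". The objectives, the enrolment paragraph and the sample size also deal with three technique groups. The data collection list includes the number of passes and any further maneuvers, but not which needle was assigned.

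The analysis section compares groups and plans a relative risk regression for adjusted differences. It adds that the regression will help to find factors associated with cellularity and yield. It gives no covariate list and does not mention needle or an interaction.

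**The concern.** A factor that is randomised, and masked from the assessor, supports a fair comparison at no extra cost in patients. Here that factor has no stated analysis and no stated place in the data set. Two things are at stake.

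First, the needle difference in adequacy may go unreported, or may appear only as a post hoc finding, although randomisation would support it as a planned one.

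Second, the primary conclusion will be stated for "slow pull vs dry suction vs wet suction techniques using the new fine needle biopsy (FNB) needles in solid lesions". BACKGROUND says that evidence on technique with these needles is scarce, so the documents neither support nor contradict a common technique effect. The trial could describe how similar the technique differences are with the two needles, and it does not plan to.

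**Working it through.** **Inputs.** From the sample size paragraph: 45% baseline, a 25-point gain (read as absolute, so 70%), two-sided pooled Z-test, 1% level, 95 per group. From the enrolment paragraph: 300 patients, hence 100 per technique. The analysis section uses 5%, so both levels are shown. The rates are stated for cellularity and are used here as a stand-in for adequacy.

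Assumption: needles are allocated 1:1 (the ratio is not stated), giving 300/2 = 150 per needle and 300/6 = 50 per technique-by-needle cell.

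**Formula.** Power = Φ[(d − z·SE0)/SE1], where d = |p1 − p2|, SE0 = √(2·p̄(1−p̄)/n), SE1 = √((p1(1−p1) + p2(1−p2))/n), and z = 2.576 at 1% or 1.960 at 5%.

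**1. The plan's own figure.** 45% vs 70%, n = 95: SE0 = 0.0717, SE1 = 0.0694, (0.25 − 2.576×0.0717)/0.0694 = 0.94, power 82.6%. This agrees with the stated figure of more than 80%. The technique comparison with needles pooled is supported as sized.

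**2. Needle contrast, 150 vs 150.** 45% vs 61%: SE0 = 0.0576, SE1 = 0.0569, (0.16 − 1.96×0.0576)/0.0569 = 0.83, power about 80% at 5%.

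**3. One technique pair within one needle, 50 vs 50.** 45% vs 70%: SE0 = 0.0989, SE1 = 0.0957. Power is 48% at 1% and 72% at 5%.

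**4. Interaction contrast.** Suppose one pair differs by 25 points with one needle and by 0 with the other. The SE of the difference in risk differences is √((3×0.45×0.55 + 0.70×0.30)/50) = √(0.9525/50) = 0.138.
- Power at 5% = Φ(0.25/0.138 − 1.96) = 44%.
- The 95% CI half-width is 1.96×0.138 = 0.27, or 27 points.
- 80% power at 5% would need about 120 per cell.
- A full reversal (+25 vs −25 points) would have about 96% power at 5%.

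**5. Effect of averaging on a pooled technique pair, n = 100 per group (illustration only).**

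| Gain with needle A / needle B | Pooled rates | Power at 1% | Power at 5% |
|---|---|---|---|
| 25 / 0 | 45% vs 57.5% | 21% | 42% |
| 25 / 15 | 45% vs 65% | 61% | 82% |
| 25 / 25 | 45% vs 70% | 85% | 95% |

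Nothing in the documents says which row is nearer the truth.

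**The case against.** The strongest case against is that the plan sets one question, technique, and that randomising needle to keep it balanced across techniques is legitimate and creates no duty to compare two products. That stands as a defence of the primary analysis. It does not explain why a randomised factor is absent from the data list, the allocation code and the named model terms.

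A reader might infer that the randomised needle comparison is discarded. The documents do not go that far. The regression's search for associated factors could include needle, and the envelope cards carry the needle assignment, so it need not be lost. The supportable statement is that needle and its interaction with technique are not named.

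A reader might also infer that the pooled technique result may hold for neither needle, or is likely to be non-significant. Because needle is randomised, the pooled contrast is a valid average whether or not the effects are equal, and no section offers evidence of interaction. The 21% figure is one extreme case. Even there, if one technique beat both others, the chance that at least one of the two pairs is significant was simulated at about 61% at an uncorrected 5% (31% at 1%).

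Two further objections limit the remedy. An interaction analysis at this size is weak, as shown. The needle contrast is also an average: if only one technique gains 25 points, and only with one needle, the contrast is 45% vs (45+45+70)/3 = 53.3%, with about 30% power at 5%. Finally, METHODS lets the endoscopist change needle or technique when three passes are suboptimal, and the official score follows once tissue is judged sufficient. Only a comparison by assigned needle is protected by randomisation, and it may be diluted.

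**Conclusion.** The concern holds as a gap in the planned analysis, not as a flaw in the primary technique test. Needle is randomised in Study Design and METHODS, but the objectives, endpoints, data list and analysis do not use it, and the allocation code omits it. The technique comparison stays valid as an average over needles.

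The needle contrast could be estimated with useful precision from the planned 300 patients. The interaction could not be settled: only something close to a full reversal would be detected reliably. These figures rest on 1:1 needle allocation, on the plan's 45% and 70% applied to adequacy, and on no loss of patients. An uneven needle ratio would lower power for the needle contrast. The averaging table shows sensitivity; it is not a forecast that technique effects differ by needle.

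**What to change.** 1. **Study Design and METHODS:** describe the 3x2 structure, state the needle allocation ratio, and make the allocation code identify the technique-by-needle cell (six codes).
2. **Data Collection:** add the assigned needle.
3. **Secondary outcome and Statistical Analysis:** add the difference in adequacy by assigned needle, with a 95% CI, as a secondary result.
4. **Statistical Analysis:** name assigned needle, and endoscopist as the stratification factor, as covariates in the planned relative risk regression.
5. **Statistical Analysis:** report the three technique differences within each needle with 95% CIs, and a technique-by-needle term, all labelled exploratory. Rely on the intervals rather than on the interaction p-value.
6. Analyse by assigned needle, whatever was used after the third pass.

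The cost is plan wording, one data field and a few table rows, with no more patients. The drawback is one more secondary contrast and an imprecise interaction estimate. These additions should be fixed before any outcome data are examined by needle; made afterwards, they would be post hoc.
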